1 INTRODUCTION

1.1 Background

[REDACTED]

[REDACTED]

[REDACTED]

[REDACTED]

[REDACTED]

[REDACTED]

[REDACTED]

[REDACTED]

[REDACTED]

[REDACTED]

[REDACTED]

[REDACTED]

[Redacted text block]

[Redacted text block]

[Large redacted text block]

1.2 Rationale

[Redacted text block]

[Redacted text block]

- [REDACTED]
- [REDACTED]
- [REDACTED]

[REDACTED]

[REDACTED]

[REDACTED]

[REDACTED]

[Redacted]

[Redacted]	[Redacted]	[Redacted]	[Redacted]	[Redacted]	[Redacted]
[Redacted]	[Redacted]	[Redacted]	[Redacted]	[Redacted]	[Redacted]
[Redacted]	[Redacted]	[Redacted]	[Redacted]	[Redacted]	[Redacted]
[Redacted]	[Redacted]	[Redacted]	[Redacted]	[Redacted]	[Redacted]
[Redacted]	[Redacted]	[Redacted]	[Redacted]	[Redacted]	[Redacted]
[Redacted]	[Redacted]	[Redacted]	[Redacted]	[Redacted]	[Redacted]

[Redacted]

[Redacted]

[Redacted]

- [Redacted]
- [Redacted]
- [Redacted]
- [Redacted]
- [Redacted]
- [Redacted]
- [Redacted]
- [Redacted]
- [Redacted]

[REDACTED]

[REDACTED]

[REDACTED]

[REDACTED]

[REDACTED]

[REDACTED]

[REDACTED]

[REDACTED]

[REDACTED]

[REDACTED]

[REDACTED]

[REDACTED]

[REDACTED]

[REDACTED]

[Redacted]

[Redacted]

[Redacted]

[Redacted]

[Redacted]

[Redacted]

[Redacted]

[Redacted]

[Redacted]

[Redacted]

[Redacted]

[Redacted]

[Redacted]

[Redacted]

[REDACTED]

[REDACTED]

[REDACTED]

- [REDACTED]

- [REDACTED]

 - [REDACTED]

[REDACTED]

[REDACTED]

[REDACTED]

[REDACTED]

[REDACTED]

[REDACTED]

[REDACTED]

[REDACTED]

[REDACTED]

[REDACTED]

[REDACTED]

[REDACTED]

[REDACTED]

[REDACTED]

[REDACTED]

[REDACTED]

[REDACTED]

[REDACTED]

[REDACTED]

[REDACTED]

[REDACTED]

[REDACTED]

[REDACTED]

[REDACTED]

[REDACTED]

[REDACTED]

[REDACTED]

[REDACTED]

[REDACTED]

[REDACTED]

[REDACTED]

[REDACTED]

[REDACTED]

- [REDACTED]
- [REDACTED]
- [REDACTED]
- [REDACTED]
- [REDACTED]
- [REDACTED]
- [REDACTED]
- [REDACTED]
- [REDACTED]
- [REDACTED]
- [REDACTED]

[REDACTED]

- [Redacted]
- [Redacted]
- [Redacted]
- [Redacted]
- [Redacted]
- [Redacted]

[Redacted]

[Redacted]

[Redacted]

[Redacted]

[Redacted]

- [Redacted]
- [Redacted]
- [Redacted]
- [Redacted]
- [Redacted]

[Redacted]

[Redacted]

[Redacted]

[Redacted]

2 TRIAL OBJECTIVES

2.1 Primary objective

To compare the efficacy of repeated slow IV infusions of DT at doses of 20 mg/m² or 30 mg/m² to Best Standard of Care (BSC) in patients with advanced HCC after failure or intolerance to Sorafenib on overall survival (OS).

2.2 Secondary objectives

- To compare DT and BSC in additional efficacy parameters as progression free-survival (PFS) and objective response rate,
- To determine the optimal dose of DT infusions;
- To evaluate the safety of DT;
- To assess PK parameters of DT at the doses of 20 and 30 mg/m²;
- To evaluate pharmacodynamics parameters and predictive factors of safety and efficacy.
- To measure QoL using a generic health-related questionnaire

3 TRIAL DESIGN

This is a multicentre, open-label, randomised, comparative, 3 arms (DT 20 mg/m², DT 30 mg/m², Best Standard of Care) study in patients suffering from hepatocellular carcinoma.

The study will be carried out at multiple hepatology or oncology centres that manage patients with HCC with or without cirrhosis. Approximately 100 centres will be involved in the trial.

Based on the survival data obtained in the phase II clinical trial, it has been calculated that 390 patients have to be included to adequately compare the efficacy of DT 20 mg/m² and DT 30 mg/m² to that of BSC.

A safety evaluation will be carried out on a regular basis at least twice a year by the Data Safety Monitoring Board (DSMB) and every 75 patients (around 25 patients/group) whichever comes first.

Patients who meet the inclusion/exclusion criteria will be randomised according to a 1:1:1 ratio to receive either DT 20 mg/m², DT 30 mg/m², or BSC. Only those patients whose survival expectations is longer than 2 months and could receive more than 1 DT infusion will be enrolled.

The study duration for each patient includes a screening period of 28 +/- 2 days maximum before baseline visit (D0 Cycle 1). The patient will then be randomised to receive either DT 20 mg/m² or DT 30 mg/m² as protracted IV infusion over 6 hours once every 4 weeks or BSC.

Patients will receive study therapy until unequivocal tumour progression (assessed by the investigator) or occurrence of unacceptable toxicity.

All patients will be evaluated by CT scan or MRI every 2 months for tumour assessments.

After study therapy discontinuation, an end of study visit will be performed 1 month +/- 7 days after the last DT infusion or last BSC treatment.

Then, a follow up of all patients (including those who withdrew prematurely from the study) will be maintained every 3 months until death. The following information will be recorded:

- Survival (patient alive or deceased)
- Date of progression (in the case of withdrawal for other reason than progression during the study treatment period)
- Administration of any other anti-cancer treatment.

The follow-up period is defined as “until 2 years after Last Patient In”.

4 SUBJECT SELECTION

The study will be carried out in patients suffering from advanced hepatocellular carcinoma (HCC), who meet all the inclusion and exclusion criteria presented in sections 4.1 and 4.2.

4.1 Inclusion Criteria

All patients included in the study will have to meet the following criteria for inclusion in the study:

1. Male or non-pregnant, non-breast feeding female;
2. Aged ≥ 18 years;
3. Patients with:
 - advanced HCC (BCLC-C according to BCLC staging classification) having progressed under Sorafenib therapy or intolerant to Sorafenib, or;
 - intermediate HCC (BCLC-B) non eligible or non responders to transarterial chemoembolization (TACE), and having progressed under or intolerant to Sorafenib therapy;
4. Patients with porta hepatis lymph nodes, extrahepatic metastases, or portal/suprahepatic vein thrombosis without extension in inferior/superior vena cava, are eligible;
5. HCC diagnosed according to the AASLD and/or EASL criteria:
 - Radiological Criteria applicable in cirrhotic liver:
 - Nodule ≥ 10 mm: one imaging technique among MRI and CT scan showing typical appearances for HCC defined as arterial enhancement and rapid washout in portal venous or delayed phase;
 - If appearance not typical for HCC on initial imaging: second contrast enhanced study (CT or MRI) showing typical appearances for HCC defined as arterial enhancement and rapid wash-out in portal venous or delayed phase;
 - And/Or cyto-histology criteria (e.g. in case of atypical lesions for HCC at imaging, absence of cirrhosis);
6. Without cirrhosis or with a non decompensated cirrhosis (Child-Pugh score from A5 to B7 included (appendix II));
7. ECOG Performance Status 0 or 1 (appendix IV);
8. Adequate laboratory tests, in particular with:
 - Platelets $\geq 50,000/\text{mm}^3$
 - Neutrophil count $\geq 1000/\text{mm}^3$
 - Haemoglobin $\geq 10\text{g/dL}$
 - Serum transaminases < 5 ULN (NCI/CTC grades 0, 1, or 2)
 - Alkaline phosphatases < 5 ULN (NCI/CTC grades 0, 1, or 2)
 - Serum bilirubin $< 35 \mu\text{M/L}$ (or 2.0 mg/dL)
9. Having given a written informed consent.

4.2 Exclusion Criteria

Exclusion criteria are as follows:

1. Cirrhosis with a Child Pugh score B8-C15;
2. Untreated chronic hepatitis B (in case of chronic hepatitis B, an efficacious antiviral treatment should be prescribed before randomisation to be included in the study);
3. Patients eligible for curative treatments (transplantation, surgical resection, percutaneous treatment);
4. Patients eligible for other efficacious treatments: TACE, Sorafenib. Patients who failed to Sorafenib treatment or intolerant to Sorafenib are eligible and can be included if Sorafenib has been stopped at least 2 weeks before randomisation;
5. Other prior malignancy without complete remission in the last five years with the exception of adequately treated basal cell carcinoma or in situ cervical cancer. In case of other prior malignancy, the diagnosis of HCC has to be histologically proven;
6. HCC developed on transplanted liver;
7. Known HIV infection;
8. Risk of variceal bleeding - i.e. patients with stage 2-3 varices with fragility signs (patients at risk for variceal bleeding) may be included after a preventive treatment (oesophageal varices ligation, beta blockers) has been administered; DT will not be administered in case of digestive bleeding in the 4 previous weeks;
9. SaO₂ < 95%;
10. Presence of a significant acute or chronic respiratory disease defined as NCI /CTCAE > grade 2;
11. Presence of recent (< 6 months) or current cardiac failure (class II, III or IV NYHA classification), baseline LVEF < LLN by either cardiac ultrasound or cardiac scintigraphy, recent (< 6 months) acute coronary syndrome, clinically significant ECG abnormalities or recent (less than 6 months) acute vascular diseases (stroke, MI...);
12. Previous cumulative dose of > 300 mg/m² of doxorubicin (or equivalent);
13. Patients currently treated with immunosuppressive agents that cannot be stopped;
14. Patient whose medical or surgical conditions are unstable and may not allow the study completion or compliance, and specially patients with uncontrolled diabetes;
15. Uncontrolled systemic infection;
16. Patient with a life expectancy of less than 2 months;
17. Patients who have received an experimental drug in another clinical trial in the last 30 days prior to randomisation in the present clinical trial;
18. (a) Women of child-bearing age who are unwilling or unable to use an effective contraception method (oral contraception or intra-uterine device for woman) during the study treatment period and for 6 months after the last administration of study drug, and their male partner(s) refusing to use a condom (if applicable),
(b) Men who are unwilling or unable to use a condom during the study treatment period and for 6 months after the last administration of study drug, and their female partner(s) refusing to use one of the appropriate effective contraception method (if applicable);
19. Patients unwilling or unable to comply with protocol requirements and scheduled visits.

4.3 Patient Registration

Enrollment will occur after informed consent has been obtained and all screening assessments have been performed.

The assignment of number and code for patient's identification will ensure patient's anonymity. Patients will be assigned a sequential patient number in each center and will be identified by:

- The identification center number (a 3-digit number)
- The patient number (a 4-digit number); these four numbers being allocated according to the sequence of presentation for trial participation in each centre.

As soon as a potential patient is screened by an investigational centre, the investigator will have to complete the eCRF. If needed, he may contact Onxeo (formerly known as BioAlliance Pharma) or its representative in order to review the inclusion criteria.

ONXEO
(formerly known as BioAlliance Pharma)

If eligibility criteria are met, patients will be included, randomised in one of the three groups :

- Doxorubicin Transdrug™ at 20mg/ m²
- Or Doxorubicin Transdrug™ at 30 mg/m².
- or Best Standard of Care.

Randomisation will be performed using IWRS with stratification on region (Europe versus United States versus other countries (Turkey, Egypt, Lebanon, Saudi Arabia)).

4.4 Subject Premature Withdrawal

In accordance with the Declaration of Helsinki as amended from time to time, subjects are free to withdraw from the study at any time if they wish so, for any reason specified or unspecified.

The criteria for enrollment must be followed explicitly. If a patient who does not meet enrollment criteria is inadvertently enrolled, that patient should be discontinued from the study and Onxeo (formerly known as BioAlliance Pharma) or its designee must be contacted. An exception may be granted in rare circumstances where there is a compelling ethical reason to allow the patient to continue taking study drug. In these rare cases, the investigator must obtain documented approval from the Onxeo (formerly known as BioAlliance Pharma) medical monitor to allow the patient to continue in the study.

In addition, a patient's participation may also be discontinued at any time at the discretion of the investigator or Sponsor. The following are some of the potential reasons that could lead the investigator or sponsor to remove a patient from the study drug or the study, or both:

- The investigator believes that a change of therapy would be in the best interest of the patient (e.g. the patient needs to be treated, for any reason, with another anti cancer therapy);
- The patient experiences an intolerable AE. An intolerable AE is an event that, even with optimal treatment, causes such discomfort or disability that the patient is unable or unwilling to continue further study participation
- The patient is non compliant with study requirements
- The patient becomes pregnant during the study or fails to use adequate birth control (for those patients who are able to conceive)
- The patient requires a medication prohibited by the study protocol
- The Sponsor decides to terminate the trial

The reason for withdrawal will have to be recorded in the e-CRF for all withdrawn subjects.

The e-CRF has to be completed until the time of drop out. All drop outs after the first intake of investigational product should be given a post-study assessment as appropriate. The premature termination form in the e-CRF must be completed for all drop outs. The survival status of all patients (including patients prematurely withdrawn) will be collected every 3 months until death with the follow-up contact

5 ENDPOINTS and ASSESSMENTS

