6.3 DT Administration

In DT groups, based on DSMB recommendation after their careful review of the safety profile reported in the first 75 patients, a shorter period of hospitalization could be recommended since

version 5.0, June 10th, 2014 as compared to the previous protocol version. The premedication will be unchanged as compared to the previous protocol version and administered to the patient according to each centre's usual practice. On D0, one day before each DT administration, patient will be hospitalized or will have an outpatient visit to check eligibility criteria for continuing treatment and to ensure that the premedication is taken. Patient will receive DT infusion on D1 and will be hospitalized until D2. Patient could be discharged on D2 or on D3 in the absence of toxicity. Hospitalization until D3 is optional.

Hospitalization or outpatient visit on D0 and prolonged hospitalization until D3 will be adapted according to hospital practice and/or patient preference.

Day 0 defined as one day before the treatment with DT

- Premedication with methylprednisolone 32 mg p.o. (or equivalent) and cetirizine 20 mg p.o.(or equivalent);

Day 1 : Day of therapy with DT

- H-1: premedication with methylprednisolone 32 mg p.o. (or equivalent) and cetirizine 20 mg p.o.(or equivalent);
- Fasting is not needed;
- **H0:** 20 mg/m² or 30 mg/m² of DT will be prepared and infused over 6 hours through intravenous route (Appendix VII).
- Patient will have a continuous SaO₂ monitoring during infusion and the 24 hours after the infusion start.

Any modification in the infusion rate must be recorded in the e-CRF (see section 7.6: safety measures).

Day 2 : The day after the DT therapy:

- Premedication with methylprednisolone 32 mg p.o. (or equivalent) and cetirizine 20 mg p.o.(or equivalent);

D0 = D28

Each Cycle will be repeated every 28 days up to progression or toxicity.

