9.2 Population to be analyzed

The Safety Population is defined as all included subjects receiving at least one DT infusion or at least one anti-cancer therapy or supportive care as BSC. For safety analyses, patients will be affected to the group of treatment they actually received.

The following populations are planned for the efficacy analyses:

- The Intent To Treat (ITT) Population : all randomized patients. In this population, patients will be analysed in their randomisation group whatever the treatment they received.
- The Per Protocol (PP) population includes all the patients of the ITT population without any major protocol deviation. Patients terminating the study prematurely will be included in the PP population provided that there is no protocol deviation. Before locking the database, the precise reasons for excluding patients from the PP dataset will be fully defined and documented by the Blind Review Committee.

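### Section 4.4 takes randomised patients found ineligible out of the study, not only off study drug, so PFS and ORR in the ITT Child-Pugh A population may lack their scans

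*Combined protocol and SAP*

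**What the plan says.** Section 4.4 (Subject Premature Withdrawal) sets the rule for a patient enrolled in error: "If a patient who does not meet enrollment criteria is inadvertently enrolled, that patient should be discontinued from the study". A rare exception needs the approval of the sponsor's medical monitor, where there is "a compelling ethical reason to allow the patient to continue taking study drug". The next paragraph, on other reasons for withdrawal, speaks of a decision to "remove a patient from the study drug or the study, or both", so the section itself distinguishes the two steps. It then ends data entry at withdrawal: "The e-CRF has to be completed until the time of drop out". It keeps one item for everyone: "The survival status of all patients (including patients prematurely withdrawn) will be collected every 3 months until death".

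Section 3 plans CT or MRI every 2 months for all patients. After therapy stops, it plans 3-monthly follow-up that records survival, later anticancer treatment and, for patients withdrawn for a reason other than progression, the progression date.

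Section 9.2 defines ITT as all randomised patients and adds: "In this population, patients will be analysed in their randomisation group whatever the treatment they received". Section 9.1.2 puts PFS and ORR in the ITT Child-Pugh A population third and fourth in the hierarchical sequence, after OS in the ITT and in the ITT Child-Pugh A populations. Under section 9.4.2 both rest on independent radiological review. PFS is censored at the last tumour assessment for patients without progression or death at the end of the study treatment period, and ORR is confined to that period.

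**The concern.** The ITT population keeps these patients, but the withdrawal rule can stop the data that two of its formally tested endpoints need. A progression date reported at a 3-monthly contact is not an image that an independent reviewer can read. A patient withdrawn before the first 2-month scan would therefore be censored for PFS at or near baseline and would have no response assessment, and the visible text does not say how such a patient counts in ORR.

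Patients who fail an entry criterion on liver function, blood counts or oxygen saturation may well have a worse prognosis than the rest. If they were removed at different rates in the arms, the PFS censoring would be informative and could move the hazard ratio. If the rates were similar, the cost would be some lost information.

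**Working it through.** **The plan's figures.** The plan gives no ineligibility rate, so there is no stated figure on this point to reproduce. The population size does reproduce: 291 / 0.90 = 323.3, rounded up to 324 Child-Pugh A patients. At 1:1:1 allocation that is 108 BSC and 216 pooled DT.

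**Patients affected (assumed 1-5%).** 324 x 0.01 = 3.2 and 324 x 0.05 = 16.2, so about 3 to 16 patients.

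**PFS, lost information only.** Assume 250 events and a hazard ratio of 0.72. Schoenfeld power = Phi(|ln HR| x sqrt(E x 1/3 x 2/3) - 1.96).
- No removal: 0.3285 x sqrt(250 x 2/9) - 1.96 = 0.489, power 68.7%.
- 5% removed in each arm: E = 237.5, power 66.5%.

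**PFS, possible bias.** Simulation with no true effect: exponential PFS with a median of 3 months (assumed), 110 BSC and 221 DT (85% of 390 is 331.5), removed patients at 2-3 times the hazard of the others, log-rank test at one-sided 2.5%. Rows 1 to 4 use 20,000 trials per setting; the last row uses 6,000 (standard error about 0.2 points).

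| Removed, DT vs BSC | Censored at | PFS HR | One-sided error |
|---|---|---|---|
| 5% vs 1% | day 0 | about 0.97 | 4.1-4.4% |
| 8% vs 2% | day 0 | 0.96-0.95 | 4.7-6.1% |
| 2% vs 1% | day 0 | not tabulated | 3.1-3.4% |
| 5% vs 5% | day 0 | essentially no bias | 2.8-3.1% |
| 5% vs 1% and 8% vs 2% | first 2-month scan | 0.98-0.99 | about 3.1-3.2% |

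Separate smaller runs of the day-0 settings in rows 1 and 2 gave 3.6-5.8%, which is consistent.

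**ORR.** Assume true rates of 2% (BSC) and 10% (DT), with unscanned patients counted as non-responders. The observed rate in an arm is p x (1 - d), where d is the share removed.
- No removal: 10.0 - 2.0 = 8.0 points, power 79.1%.
- 1% removed in each arm: 9.90 - 1.98 = 7.9 points, power 78.6%.
- 5% removed in each arm: 9.5 - 1.9 = 7.6 points, power 76.4%.
- 5% of DT and none of BSC: 9.5 - 2.0 = 7.5 points, power 74.8%.

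Under this counting rule, more removal in DT works against DT.

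**The case against.** Three stronger readings are tempting, and the documents support none of them.

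- A reader might infer that section 4.4 contradicts the ITT definition. It does not. Leaving the study is not leaving the analysis set; section 9.2 keeps every randomised patient, and sections 3 and 4.4 keep survival follow-up after withdrawal.
- A reader might infer that removal is more frequent in DT, because before each infusion the "patient will be hospitalized or will have an outpatient visit to check eligibility criteria for continuing treatment". Those are the continuing-treatment criteria of section 6.6.2. Several of their thresholds match entry criteria, so re-testing might bring an entry error to light. But failing them leads to a delay and then withdrawal from the study treatment period, not to the section 4.4 rule. Entry eligibility is settled before randomisation in all arms, and the synopsis puts BSC visits on the same schedule.
- A reader might infer that the exception is open only to DT because it mentions study drug. The sentence that follows speaks of continuing in the study, and the synopsis uses study drug for the control group's end visit too.

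Other points on that side have weight. The sections on endpoints and follow-up (5.1-5.3, 7.2.3-7.2.5) cannot be read in the public version. Section 3 plans scans for all patients. Section 9.1.1 leaves missing data to a separate SAP, and section 9.4.2 refers PFS censoring to FDA guidelines. Continued scanning may therefore be provided for somewhere; if so, section 4.4 still has to be reconciled with it.

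The PFS error above is also that of one test taken alone. PFS is tested only after OS succeeds twice, so if DT has no effect on OS the sequence still limits the overall error. The inflation matters only if OS truly improves and PFS does not.

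What stands is that the visible rule says study where the same section knows the difference from study drug, and that a reported progression date cannot replace a reviewed scan.

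**Conclusion.** The point holds as a gap in data collection for PFS and ORR, and fixing it is a cheap improvement. OS is largely protected. For PFS the bias is probably small, and its size and direction depend on how many patients are found ineligible and whether the arms differ, neither of which the documents give.

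A one-sided error of about 4-6% for the PFS test needs three assumptions together: removal of 5-8% in DT against 1-2% in BSC, two to three times the hazard in those removed, and censoring on day 0. Relaxing either the imbalance or the day-0 censoring brings it to about 3%. With equal removal the main cost is power: about 2 points for PFS and 3 points for ORR at 5% removed in each arm, under the assumed effects.

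**What to change.** 1. **Section 4.4.** Separate stopping study treatment from leaving the study. Whether such a patient goes on with study treatment stays with the protocol and the medical monitor. State that, unless consent is withdrawn, these patients in all three arms keep the 2-monthly scans for independent review until progression, AE reporting and survival follow-up, and that the e-CRF stays open for these data.
2. **Section 9.4.2, PFS.** Count these scans instead of censoring at the end of the study treatment period. Without this, the extra scans might be collected and then not used.
3. **Section 9.4.2, ORR.** Count ITT patients with no post-baseline scan as non-responders.
4. **Reporting.** Give the number found ineligible after randomisation by arm. Sections 9.1.4 and 9.1.5 already plan to check eligibility and to examine deviations from the entry criteria, so this adds one line to a table.

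The cost is a few sentences in the protocol, and continued scans and visits for a small number of patients.
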